Rationale / context	
Assessment of health status and physical function is fundamental in patients with obesity, as they play an important role among the various factors influencing quality of life in this population (1). Several studies have shown an association between high BMI values and a significant deterioration in quality of life, especially in women (1). Excess body fat in obese patients seems to be responsible for muscle atrophy. This causal link is probably related to dysfunctions in adipose tissue, leading to a decrease in the expression of proteins responsible for muscle contraction (2). Recent literature highlights an alteration in quality of life, particularly in obese and elderly subjects, for which changes in muscle function are partly responsible. Changes in muscle function can be assessed by simple, rapid and non-invasive tools. They could allow the identification of obese subjects at risk of at risk of muscle atrophy, stratify the risk, and propose the implementation of a prophylactic intervention or an early management.

Main Objective	The main objective of this study is to evaluate the association between structural alteration of the quadriceps and quality of life in obese patients.
Secondary objectives	
Secondary objectives are to assess:
 
 - The association between quadriceps thickness and quality of life; - The association between grip strength and quality of life; - The association between quadriceps strength of the quadriceps and quality of life;

	
 - The association between quadriceps strength and ultrasound measurements of the quadriceps.
Research Diagram	Prospective, monocentric, interventional cohort study with minimal risks and constraints falling within the scope of article L.1121-1 of the Public Health Code.
Inclusion criteria	
 - Obese patient (BMI > 30) consulting a Nutrition Day Hospital (HDJ); - Patient at least 18 years of age at the time of inclusion; - Affiliation with a social security system or beneficiary of such a system ; - Oral, free, informed and express consent of the patient.
Non-inclusion criteria	
 - Patient refusal to participate in the study; - Known pregnancy; - State of Consciousness Incompatible with Obtaining Consent; - Person subject to a safeguard of justice measure ; - Patient under guardianship or curatorship.
Primary endpoint	The primary endpoint was the association between femoral rectus muscle echogenicity and the SF-36 quality of life score.
Secondary endpoints	
The secondary evaluation criteria will be:
 
 - The association between ultrasound thickness of the femoral rectus and the SF-36 quality of life score; - The association between grip strength measured by the handgrip and the SF-36 quality of life score; - The association between quadriceps Voluntary Maximum Strength (VMS) on dynamometry and SF-36 quality of life score; - The association between quadriceps FMV with dynamometry and ultrasound measurements of the rectus femoris (thickness, echogenicity, and cross-sectional area).
Intervention	Patients will be clinically assessed for muscle function: FMV and handgrip. A muscle ultrasound and a quality of life score will also be performed in the included patients.
Number of subjects needed	84

Expected number of centers	1
Duration of the research	9 months
Statistical analysis of the data	
Statistics will be primarily descriptive and will be based on means (+/- standard deviation) or medians [minimum-maximum] depending on the distribution of quantitative variables. Qualitative variables will be described in terms of numbers and percentages. Univariate comparisons will use the usual statistical tests after verification of the distribution of the variables (Chi2 or Fisher's test, t-test, anova or their non-parametric equivalents Wilcoxon and Kruskal-Wallis tests).
 
Tests will be performed at the 5% significance level. The 95% confidence intervals will be provided for each estimate. Measures of association between categorical variables will be performed using the Chi-square or Fisher test depending on the distribution of the data. Calculations will be done using SPSS v21 IBM and R software (version 3.6.1, www.R-project.org).

Expected benefits	
This study will evaluate the association between peripheral muscle function and quality of life impairment in obese patients hospitalized in HDJ Nutrition. These results will confirm the association between muscle status and quality of life in obese patients, which is not yet clear in the scientific literature. If necessary, these results will make it possible to propose non-invasive and inexpensive tools to screen for muscle damage in this patient population. This screening could allow to propose early management programs.

1.1 Obesity, a global public health issue

Obesity is a disease characterized by an excessive and abnormal accumulation of body fat, associated with adverse health effects. Obesity has become a global public health problem and is responsible, according to the World Health Organization (WHO), for at least 2.8 million deaths (3) and is recognized as the fifth leading cause of death in the world. The number of obesity cases has almost tripled since 1975.

In France, obesity affects 17% of adults and, among children, 16% of boys and 18% of girls (4). In parallel with the progression of obesity at the global level, the WHO declared in 2014 the risk of the accumulation of diseases, including the coexistence of undernutrition and obesity.

Obesity is a disease of multifactorial origin, linked to nutritional alterations, genetic, psychological, socio-economic factors and more sedentary behaviors (4) (5). The prevalence of obesity continues to increase in all age groups and in all socioeconomic groups. It is a major risk factor for a range of diseases, including type 2 diabetes, cardiovascular disease and certain types of cancer (6). People with obesity also have impaired health-related quality of life and higher mortality compared to healthy people (7). Excess adipose tissue has implications for physical disability, including changes in gait pattern and/or decreased functional capacity (8). These repercussions may be of peripheral muscular origin, with consequences for mobility and independence in activities of daily living (ADL's) (9).

1.2 Functional consequences of obesity

1.2.1 Quality of life

The impact of obesity on quality of life has been assessed by several studies. According to the WHO, quality of life is how individuals perceive their position in life, in the context of the culture and value system in which they live and in relation to their goals, expectations, norms and concerns. It is a broad concept, incorporating in complex ways a person's physical health, psychological state, degree of independence, social relationships, personal beliefs, and relationship with important elements of the environment (10) (11).

The assessment of health status and physical function is fundamental in patients with obesity, as they play a major role among the various factors that will influence their quality of life (1). Several studies have shown an association between high BMI values and a significant deterioration in quality of life, especially in women, mainly related to an increase in pain. In

addition, people with obesity have been identified as being more likely to suffer from depression and/or mood disorders (1).

According to Kim et al. (2020) patients with obesity with or without a metabolic disorder have health alterations including mental problems and decreased quality of life (12). In younger obese subjects we also observe a decrease in quality of life compared to normal weight subjects, where muscle capacity may be a potential factor associated with impaired quality of life (13).

1.2.2 Peripheral muscle damage

Obese individuals have greater muscle mass and higher muscle strength than non-obese individuals. However, this increase in muscle strength is not proportional to the increase in total body mass, so that body weight-adjusted strength is lower in obese individuals than in nonobese adults (14). The increase in muscle mass in obese individuals results from the increased load imposed by body weight, which acts as a chronic stimulus to muscle tissue (15). Contrary to the benefits of resistance exercise, excess body fat does not appear to be a sufficient load stimulus to alleviate the functional consequences of obesity (difficulty walking, cycling, standing from a chair) (16).

In addition, a decrease in the specific force of the muscle is observed in obese subjects, i.e. a decrease in the force related to the sectional area. There is therefore probably a structural alteration of the muscle in the obese patient, which has not yet been well described in the literature (17). The quantity of muscle fibers decreases and is replaced by infiltration of adipose and fibrous tissue. (17). This replacement of skeletal muscle fibers decreases muscle quality and increases density, thus altering its function. The reduction in muscle mass relative to fat mass, results in a relative loss of muscle strength available to support and move body weight (17). In elderly subjects with obesity the amount of fat mass is strongly and negatively correlated with leg extension strength ($r = -0.825$) (18) with a negative impact on physical functioning and quality of life (19).

Moreover, an alteration in muscle contractile proteins coexists or occurs in a second stage in obese subjects, which can lead to muscle atrophy. Indeed, the expression of inflammation factors (IL-6 and IL-1b) by adipocytes leads to a decrease in the expression of genes coding for muscle contraction proteins, including troponin, titin and myosin (20).

The association between lower limb function, including walking ability, and health-related quality of life has been studied in young subjects with obesity, finding that a decrease in this ability correlates with impaired quality of life (13).

1.3 Ultrasound of the peripheral muscle

Muscle ultrasound measurements have become increasingly used as a noninvasive method to determine muscle characteristics (21). Muscle characteristics, particularly muscle size and quality, have been shown to be related to muscle strength and power as well as cardiovascular performance. Ultrasound can also measure muscle echogenicity. The echogenicity of a B-mode (2D) ultrasound image is expressed by a gray scale (22). On an ultrasound image, the muscle bundles are hypoechoic areas, whereas the aponeuroses are hyperechoic. In the case of atrophied muscles, represented by hyperechoic structures, there is a decrease in the ability of ultrasound to penetrate deep into the tissue (23). Thus, the replacement of skeletal muscle fibers by fatty infiltrates decreases muscle quality and increases its density, thus increasing the echogenicity of ultrasound images (17). Muscle thickness is used to estimate the degree of atrophy (24). Ultrasound thickness of the rectus femoris has been shown to be strongly correlated with muscle cross-sectional area (mCSA) (25). More recently, mCSA has been described as strongly correlated with muscle function. Accurate assessment of mCSA may be a tool for predicting strength, muscle power, overall health, and quality of life (21). It would appear that measurement of muscle echogenicity of the rectus femoris would be more valid for assessing muscle quality. According to Wilhelm et al. (2014) there is an inverse relationship between quadriceps echogenicity and functional capacity, suggesting that the accumulation of non-contractile elements within the muscle may be a mechanism related to non-neurological muscle loss (9).

In the obese subject, ultrasound allows for improved analysis of muscle tissue by assessing the amount of muscle tissue versus non-muscle tissue (22).

Loss of muscle strength combined with excessive body weight significantly impairs the ability to perform activities necessary for independence in daily living and proper body function (16). Choi et al (2015) showed that people with obesity, especially older individuals, are at increased risk for falls and functional decline (26). Thus, there is a decrease in exercise tolerance in subjects with obesity, the origin of which is multifactorial. The relative loss of muscle strength leads to greater fatigue during exercise and significantly limits the ability to perform the activities necessary to ensure independence in daily life (16). Peripheral muscle function requires the use of different assessment tools. Muscle capacity assessment tools, such as dynamometry or ultrasound, can be used to evaluate the different aspects of muscle function impacted by obesity (27).

2 Originality of the research

Excess body fat in obese patients appears to be responsible for muscle atrophy. This causal link is probably related to dysfunctions in adipose tissue, leading to a decrease in the expression of proteins responsible for muscle contraction (2). The recent literature highlights an alteration in quality of life, particularly in obese and elderly subjects, for which changes in muscle function would be partly responsible. In the general population of patients with obesity, especially adults and active people, this association has never been described and its mechanisms remain to be confirmed.

Changes in muscle function, and its association with impaired quality of life, can be assessed by simple, rapid and non-invasive tools. This will allow the identification of obese subjects at risk of muscle atrophy, stratify the risk, and implement prophylactic intervention or early management.

3 Research hypothesis

We hypothesize that impaired peripheral muscle function is associated with impaired quality of life in subjects with obesity.

4 Objective

4.1 Main objective

The main objective of this study is to evaluate the association between structural alteration of the quadriceps and quality of life in obese patients.

4.2 Secondary objectives

Secondary objectives are to assess:

- The association between quadriceps thickness and quality of life;
- The association between grip strength and quality of life;
- The association between quadriceps strength and quality of life;
- The association between quadriceps strength and ultrasound measurements of the quadriceps.

5 Judging criteria

5.1 Primary endpoint

The primary end point was the association between femoral rectus muscle echogenicity and the SF-36 quality-of-life score (**Appendix 1**).

5.2 Secondary endpoint

Secondary endpoints will be:

- The association between ultrasound thickness of the femoral rectus and the SF-36 quality of life score;
- The association between grip strength measured by the hand-grip and the SF-36 quality of life score;
- The association between quadriceps Voluntary Maximum Strength (VMS) on dynamometry and SF-36 quality of life score;
- The association between quadriceps FMV at dynamometry and ultrasound measurements of the rectus femoris (thickness, echogenicity, and mCSA).

5.3 Inclusion criteria

Patients with the following criteria will be included:

- Hospitalized in day hospital (HDJ) Nutrition;
- Obese patient (BMI > 30);
- Patient at least 18 years of age at the time of inclusion;
- Affiliation with a social security system or beneficiary of such a system ;
- Oral, free, informed and express consent of the patient.

5.4 Non-inclusion criteria

Patients with the following criteria will not be included:

- Patient refusal to participate in the study;
- Known pregnancy;
- Patient whose state of consciousness is not compatible with obtaining consent;
- Person subject to a safeguard of justice measure ;
- Patient under guardianship or curatorship.

5.5 Recruitment procedures

[figure not shown]
Patients will be recruited prospectively and consecutively in the HDJ Nutrition of the Forcilles Hospital. The physiotherapist or the investigating physician working in HDJ identifies the patients at their admission.

6 Research design

6.1 Type of study

This is a prospective, monocentric, interventional cohort study with minimal risks and constraints falling within the scope of article L.1121-1 of the Public Health Code. The research will be conducted in accordance with the protocol.

6.2 Research diagram

6.3 Provisional research schedule

The duration of recruitment will be 9 months with a follow-up of patients for one day, for a total estimated duration of the study of 9 months:

- Submission to PPC: January 2022
- Start of inclusions: March 2022
- Duration of the inclusion period: 9 months
- Duration of participation of each patient: 1 day
- End of inclusions: January 2023
- Total duration of the research: 9 months
- Communication in congresses: Scientific days of the AFERO, other scientific congresses
- Publication: international journal with review committee.

6.4 Location of the study

The study will take place in the HDJ Nutrition of the Forcilles Hospital.

7 Description of the usual care in HDJ Nutrition

7.1 Description of the usual course of care

A total of 4 patients are admitted every Monday of the week and the last Thursday of the month. Patients are hospitalized for one day. The day begins with the reception of the patient by the nurse and continues with :

- A dietary consultation;
- A psychological consultation;
- Medical consultation;
- A consultation by the physiotherapist;
- A cardiological consultation.

After the various consultations, a summary meeting is held with the doctor, nurse, physiotherapist, psychologist and dietician. This meeting allows us to define the therapeutic strategy that will be proposed to the patient.

At the end of this meeting, the nurse receives the patient in consultation and informs him of the therapeutic proposals. Finally, the patient is received by the doctor in charge who gives him the hospitalization report. All the examinations and consultations are carried out within the usual framework of the HDJ Nutrition and are systematically prescribed by the doctor in charge.

7.2 Standard evaluation procedures

7.2.1 Hand Grip Force

The maximum grip force of both hands will be measured with the portable hydraulic dynamometer JAMAR® (*Sammons Preston Rolyan Nottinghamshire, UK*) (**Appendix 2**). The dynamometer is adapted to each patient: adjustment of the hand allowing the flexion of the metacarpophalangeal joints. The grip force is obtained in kilograms (kg).

The evaluation protocol consists of three maximum voluntary isometric contractions to be held for 5 seconds, with a minimum rest period of 60 seconds. The highest value will be used to determine the maximum grip strength. The patient is placed in a seated position, with the back against the back of the chair and the feet flat on the floor. The arm position is standardized with the shoulder in adduction and neutral rotation, the elbow bent at 90°. The forearm is placed in a neutral position and rests on the support surface. The hand is aligned with the forearm.

Specific verbal instructions and encouragement are given to the patient.

7.2.2 Maximum Voluntary Force (MVF) of the quadriceps

The FMV of the quadriceps will be measured using the MicroFet 2 dynamometer® (**Appendix 3**). The patient is positioned in a seated position with the hip and knee flexed to 90 degrees. The dynamometer is positioned on the anterior surface of the ankle. The patient is asked to extend the knee to the maximum. Three maneuvers will be performed, with 30 seconds of rest

between each. The maximum value of the 3 measurements, which vary by less than 10%, will be retained.

8 Evaluation procedures added by research

8.1 Muscle ultrasound

8.1.1 Operator training

Ultrasound measurements are performed by one of the investigating physical therapists. The physiotherapist is authorized to perform ultrasound subject to training (Avis du Conseil National de l'Ordre des Masseurs-Kinésithérapeutes (2015)). The training of the operator corresponds to the following:

- 3 days of theoretical and practical training;
- Over 100 ultrasounds supervised by an experienced practitioner;

Similarly, all the physiotherapists performing the ultrasound scans are already involved in other research projects using lung, diaphragm and peripheral muscle ultrasound:

<https://clinicaltrials.gov/ct2/show/NCT02474797>,

<https://clinicaltrials.gov/ct2/show/NCT02881814>,

<https://clinicaltrials.gov/ct2/show/NCT04373811>

and

<https://clinicaltrials.gov/ct2/show/NCT04800783>.

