10.1 Calculation of the study size

Two groups of patients will be identified within our obesity patient population: a group of patients with low quality of life and a group with high quality of life. The median SF-36 quality of life score will be used to differentiate these 2 groups.

The echogenicity of the rectus femoris will be compared between these 2 groups, in order to evaluate the association between the muscular alteration of the rectus femoris by measuring echogenicity and the quality of life.

To our knowledge, no publication has evaluated the echogenicity of the rectus femoris in a population of obese patients. In the literature, an echogenicity of the rectus femoris of 120.9 ± 15.4 was found in a population of elderly patients (25). Given the presence of common pathophysiological mechanisms and similar sonographic characteristics (thickness and mCSA) in muscle damage between the elderly and obese patients, we hypothesize that the echogenicity of the rectus femoris in obese patients is similar to that in the elderly patient group with low quality of life.

In the absence of clinically relevant echogenicity difference data, we pragmatically expect a difference of at least 10 points (based on the alteration in muscle echogenicity of the resuscitation patient in 7 days (28)).

Thus, with a risk $\alpha = 0.05$ and a power of 90%, the number of subjects needed, for a two-sided test is 42 patients per group, or 84 in total.

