10.2 General aspects

Statistics will be primarily descriptive and will be based on means (+/- standard deviation) or medians [minimum-maximum] depending on the distribution of quantitative variables. Qualitative variables will be described in terms of numbers and percentages. Univariate comparisons will use the usual statistical tests after verification of the distribution of the variables (Chi2 or Fisher's test, t-test, anova or their non-parametric equivalents Wilcoxon and Kruskal-Wallis tests).

The risk of low quality of life in the presence of impaired muscle function will be described by Odd-Ratios.

Tests will be performed at the 5% significance level. The 95% confidence intervals will be provided for each estimate.

Calculations will be done using SPSS v21 IBM and R software (version 3.6.1, www.R-project.org).

11 Expected results in terms of scientific and professional advances

This study will evaluate the association between peripheral muscle function and quality of life impairment in obese patients hospitalized in HDJ Nutrition.

The results of this study will confirm the association of muscle status on quality of life in obese patients, which is not yet clearly established in the scientific literature. If applicable, these results will make it possible to propose non-invasive and inexpensive predictive tools to screen for muscle damage in this patient population. This screening could make it possible to propose early management programs, such as exercise re-training or the introduction of adapted physical activity.

12 Expected benefits and risks for patients

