16.4 Appendix 4: Muscle ultrasound procedure

A linear probe will be used for the measurements. A set of predefined settings of the gain and depth parameters will be used for all measurements.

Patient positioning

The patient is installed in dorsal decubitus (as strict as possible), with the lower limbs in extension and neutral position of rotation.

Placement of the probe

The probe is placed in contact with the skin via an ultrasound gel. The pressure exerted with the probe is perpendicular to the plane of the bed, in line with the femur and must be as low as possible to obtain a representative image of the muscle. Excessive pressure will cause deformation of the subcutaneous tissues and therefore of the muscle. There are two ways of orienting the probe: in the transverse or sagittal plane.

Measurements on the quadriceps

[figure not shown]

Figure 1

The probe is placed on the anterior aspect of the thigh, 2/3 of the way from the anterior superior iliac spine to the upper edge of the patella, plumb with the femur (**Figure 1**) (39). The muscle chiefs studied were the rectus femoris and the vastus intermedius.

[figure not shown]

Figure 2

Muscle thickness

In the transverse plane, measurement of the distance between the upper and lower fascias of the muscle body (Figure 2). It is measured directly on a frozen image. The thickness of the rectus femoris (DF) and the vastus intermedius (VI) will be measured on the right. The average of 3 measurements will be taken.

[figure not shown]

Figure 3

Cross-Sectional Area (CSA):

Still in the transverse plane, measure the cross-sectional area of the rectus femoris using the caliper to delineate the boundaries of the rectus femoris (Figure 3).

Pennation angle

Place the probe along the axis of the muscle. The angulation of the muscle fibers in relation to the underlying fascia becomes visible (pennation of the fibers (Figure 4). The angle between a muscle fiber and the underlying fascia will be measured only on the rectus femoris:

[figure not shown]

Figure 4

Echogenicity

Save the image used to measure the thickness and cross-sectional area. In the Image J software, delimit a 1 cm area² and analyze the variations of the gray levels. The software provides a histogram with a global value of the grey level going from 0 to 255 - 0 corresponding to black and 255 to white (28).

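### Several physiotherapists may acquire the echogenicity images, but neither scanner nor reader is listed for recording and the primary comparison has no operator term: a cheap improvement

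*Combined protocol and SAP*

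**What the plan says.** **Who scans.** Section 8.1.1: "Ultrasound measurements are performed by one of the investigating physical therapists". The same section adds that "all the physiotherapists performing the ultrasound scans are already involved in other research projects". So more than one scanner is foreseen. Neither their number nor a rule for assigning them to patients is given.

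**What protects the measurement.** Section 8.1.1 requires three days of training and over 100 supervised scans. Section 8.1.2 and Appendix 4 fix the patient position and the probe site. Appendix 4 also presets gain and depth, asks for minimal probe pressure, and warns: "Excessive pressure will cause deformation of the subcutaneous tissues and therefore of the muscle". It has the image saved.

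**Who reads.** Section 8.1.2 and Appendix 4 describe the Image J step without naming a reader or mentioning masking to SF-36. They disagree on the region: section 8.1.2 takes the whole muscle area, Appendix 4 a 1 cm² area.

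**What is recorded.** The data lists in sections 9.2 and 9.3 and the table in 9.5 contain no operator or reader code.

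**What is analysed.** Section 10.1 compares echogenicity between two groups formed by splitting at the median SF-36 score. Section 10.2: "Univariate comparisons will use the usual statistical tests after verification of the distribution of the variables". No operator term and no inter-operator check is planned.

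**The concern.** Grey level is the primary variable, and by the protocol's own account the image depends on how the probe is held. If physiotherapists differ systematically, two things can follow.

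- **Noise.** Operator differences spread equally over the two SF-36 groups widen the SD and cost power.
- **Bias.** If one operator scans relatively more patients in one group, part of that operator's offset appears as a group difference. Nothing in the design prevents this. The groups come from a median split, not randomisation, and assignment of operators is not described. The SF-36 is completed at the same physiotherapist visit (9.3) and may be interviewer-administered (8.2), so one person could affect both variables.

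Reading and acquisition differ in what can be repaired later. A saved image can be read again by one person. Probe pressure, angle and placement are fixed once the image is taken, and adjusting for them requires knowing who took it.

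**Working it through.** **Inputs from the documents**
- Significance level: "Tests will be performed at the 5% significance level" (10.2).
- Size: "a power of 90%, the number of subjects needed, for a two-sided test is 42 patients per group" (10.1).
- Difference: "we pragmatically expect a difference of at least 10 points" (10.1).
- SD: "an echogenicity of the rectus femoris of 120.9 ± 15.4 was found in a population of elderly patients" (10.1).
- Operator effect: not given. Everything about its size below is an assumption, shown as a range.

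**Step 1. The plan's own figure.** n per group = 2 × SD² × (z₀.₉₇₅ + z₀.₉₀)² / difference² = 2 × 15.4² × (1.960 + 1.282)² / 10² = 49.8, so 50 (51 with the t-test), or 100 to 102 in total. The stated 42 per group is not reproduced. At 42 per group the standard error is 15.4 × √(2/42) = 3.36, and 10/3.36 = 2.98. Two-sided power is then 84.5% by the normal approximation and 83.7% by the t-test. This shortfall is a separate matter; here it means there is little power to spare for extra measurement noise.

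**Step 2. Operators are already part of the 15.4.** Let share f of the variance be due to operators. Removing it gives SD = 15.4 × √(1 − f). Two-sided t-test, 42 per group, difference 10:

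| f | SD | Power |
|---|---|---|
| 0 | 15.4 | 83.7% |
| 5% | 15.0 | 85.5% |
| 10% | 14.6 | 87.3% |
| 20% | 13.8 | 90.8% |

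**Step 3. Operators come on top of the 15.4**, unrelated to SF-36 group. Total SD = √(15.4² + operator SD²). Power without an operator term:

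| Operator SD | Total SD | Normal approx. | t-test |
|---|---|---|---|
| 0 | 15.4 | 84.5% | 83.7% |
| 3 | 15.69 | 83.2% | 82.3% |
| 5 | 16.19 | 80.8% | 79.9% |

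With an operator term the residual SD returns to 15.4, but the variance of the group contrast is multiplied by 1/(1 − r²), where r is the correlation between operator and group. For two operators:
- balanced: r = 0, power 84.5% (normal approximation);
- 40/60 split: r = 0.2, factor 1/(1 − 0.04) = 1.042, power 83.0%.

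So with a small operator effect and an uneven split, the term gains no power (83.0% against 83.2%). What it does then is remove bias.

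**Step 4. Bias.** Two operators with offset D, scanning shares 0.40 and 0.60 of the two groups:
- bias = D × (0.60 − 0.40);
- standard error = √[2 × (15.4² + D² × 0.4 × 0.6)/42].

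D = 5: bias 1.0, standard error 3.40, ratio 0.29, two-sided type I error 6.0%.

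D = 10: bias 2.0, standard error 3.53, ratio 0.57, two-sided type I error 8.8%.

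With a 50/50 split, bias is 0 and type I error is 5% for any D. The only cost is power: 83.6% at D = 5 and 80.8% at D = 10 (normal approximation).

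**The case against.** The protocol takes real care over acquisition. Operators are trained, settings are fixed, position and site are standardised, and the warning in Appendix 4 concerns excessive pressure and follows an instruction to press as lightly as possible. A 10-point offset equals the whole target difference and may be implausible between such operators. No document describes operator rotas or a patient mix that varies by admission day. The SD of 15.4 comes from an outside elderly population, and nothing shows that it contains any operator variance, so a power gain above 84% may not exist.

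All of this stands as a limit on size. None of it measures residual operator differences or allows adjustment for them.

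A reader might also infer more than the documents support:
- **That operator differences can never be removed.** Reading differences can, because the image is saved. The limit applies only to acquisition.
- **That several people trace the images.** No reader is named; one person may already do it all.
- **That operator identity goes unrecorded.** The case report form is not among the documents. It can be said only that identity is not listed for recording.
- **That the primary comparison is biased.** Bias needs operators spread unevenly over the SF-36 groups, which is possible but not shown.

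**Conclusion.** The point holds as a cheap improvement, not as a demonstrated flaw in the result. The plan foresees several scanners, names no reader, lists neither for recording, and compares echogenicity without an operator term.

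Its size depends on assumptions that the documents cannot settle. If operators already account for 5–20% of the variance behind 15.4, adjustment lifts power from about 84% to 85–91%. If they account for none of it, a between-operator SD of 3–5 points takes unadjusted power to about 80–82%, and adjustment restores about 84% with balanced operators and slightly less with an uneven split. With two operators 5–10 points apart and split 40/60 across the groups, bias is 1–2 points against a target of 10, and type I error is about 6–9% instead of 5%. With balanced operators there is no bias, only lost power.

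**What to change.** - **Section 9.3:** record a scanning-operator code and a reader code for each patient.
- **Section 8.1.2 and Appendix 4:** first reconcile the region to be read, since a single reader cannot otherwise know what to delimit. Then have one existing trained investigator, masked to SF-36, read all saved images using that one defined region.
- **Section 10:** compare echogenicity with a linear model containing SF-36 group and scanning operator, and report the adjusted group difference with its 95% confidence interval.

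The cost is two data fields, a task allocation among existing staff and one model factor, with no extra patients or visits. The downsides are about one degree of freedom per extra operator, a small loss of precision if operators are unevenly spread (variance factor 1.042 at 40/60), and reading concentrated on one person. The codes should be in place before enrolment, because they are hard to reconstruct reliably afterwards.
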